There are many methods of noninvasive urine collection. These methods are preferred as they are fairly well tolerated by patients, less distressing to parents, cost effective, and require less technical expertise. In the past; these methods have been dismissed due to their high rates of contamination, time to void and also effectiveness. The National Institute of Health and Clinical Excellence (NICE, UK) recommends a clean-catch urine (CCU) be the first attempt at obtaining a urine specimen from children suspected of having UTI [2]. This means placing the urine specimen collection container into the urine mid-stream once the child has begun to void to avoid contamination. Conversely, the American Academy of Pediatrics recommends clean

catch urine for screening and a catheter specimen urine collection or suprapubic aspiration for definitive diagnosis [3]. Both of these invasive techniques produce quick urine samples with low rates of contamination; however they can be painful and distressing to both the patient and parent.

The Quick-Wee method for noninvasive urine collection has been evaluated in a one randomized controlled trial and has been shown to significantly increase the five minute voiding success rate for CC urine collection; 31%, n= 174. However a past study demonstrated contamination rate of 27%, n=174. No study has directly evaluated the use of antiseptic solution in the evaluation of the QW rate of contamination in pediatric patients. The purpose of this study is to see whether the use of povidone iodine swabs prior to the QW method will decrease the rate of contamination. A decrease of the rate of contamination would strengthen the validity of this simple CCU method. Also using the this method for the collection method in both the experimental and control groups will further evaluated the five min void success rate.

We chose to use iodine as our prepping agent because it is currently the standard cleaning solution used for adult and pediatric patients. It is readily available, inexpensive and has been shown to be less caustic then other prepping agents.

Bibliography:

1. Shaw, K. N., Gorelick, M., McGowan, K. L., Yakscoe, N. M., & Schwartz, J. S. (1998). Prevalence of urinary tract infection in febrile young children in the emergency department. *Pediatrics*, *102*(2), e16-e16.

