3. RESEARCH DESIGN AND METHODS

Research Design and Methods:

Male and Female DoD beneficiaries, aged one month (28 days) to 12 months (365 days), meeting the inclusion/exclusion criteria will be offered an opportunity to participate. Each child will already be scheduled for a standard of care urinalysis collection procedure through their pediatric PCM. They will be recruited from the clinics located at the 99MDG through direct contact with the infant’s parents. All of the below items are research-related unless marked as ‘standard of care’:

The study will be a non-blinded randomized controlled trial with parallel assignment of groups, taking place in the pediatric and emergency departments. The subject’s parents will be asked if the patient has had an allergic reaction to iodine in the past prior to being placed in experimental group and if they have had a reaction in the past they will be placed in the normal saline group instead. Additionally, if the patient develops a reaction to iodine during testing then they will have the region cleansed with normal saline, will be evaluated by the medical staff performing the test, then the urine and subject’s data will be disposed of and excluded from the study. The experimental group will have their periurethral region cleansed with povidone iodine solution while the control group will be prepped with cold (2°C) normal saline. Both groups will have the urine collection performed utilizing the QW method (see attached flow chart). If a sample is not collected within five minutes with the QW method it will be documented as a failure and the child will be referred back to their pediatric PCM and removed from the study. Urine collection will occur at the hospital.

Utilizing sequentially numbered opaque sealed envelopes (SNOSE), children will be randomly assigned to one of the two treatment groups. The envelopes will contain plastic forceps, gauze, and a 3x5 index card listing the group the child has been assigned, i.e., iodine or normal saline, as well as child’s ID number; For the experimental group there will be a package of iodine swabs and the control will have a normal saline flush. Also contained within the envelope will be the Participant Data Sheet to provide an easy way to track the urine collection process for the study..

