Parent consent will be acquired via the written consent forms prior to the initiation of any research activities.

Benefits:

There may be decreased levels of urine contamination in either the saline or the iodine prep group's urine sample. If so, this will give a child's treatment team more reliable test results and decrease the need for more invasive urine testing. Additionally the normal saline preparation may be effective at decreasing the level of contamination as the iodine, this is the benefit of using normal saline for a preparation and comparing it to the iodine.

Risks:

Procedure is safe and the only possible negative outcome could be skin irritation from the iodine prep group. There are risks that urine sample may show that there was growth of bacteria on culture in which event the parents will be contacted by the PI or AI and made aware of these results and will be advised to follow up with their pediatrician. There is a possibility that the child has an allergic reaction to the iodine swab. If this occurs, the child will be referred to their pediatric PCM. The urine sample collected during the QW procedure will still be used for the study. There may be a risk of inadvertent breach of confidentiality.

Costs: None

Safeguards for Protecting Information:

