	Specimens	Urine samples will be disposed of by the lab after analysis is complete. Results will be acquired through CHCS using the child's DoD ID# and name. DoD ID# will be used initially for urinalysis results tracking and then Study code IDs will be used for de-identified research data
	Long-term storage (following completion of the study and inactivation of IRB approval)	The research data will be coded and any links to identifiable data will be destroyed (an approved shredding bin) as soon as possible or no later than at the closure of the study, with the exception of those parents that consented to place their child's de-identified research data into the "Mike O'Callaghan Military Medical Center General Research Data Repository" (FWH20180064H) for future research. The anonymized

		research data will not be utilized for further research activity beyond the protocol stipulations without additional IRB approval. All de-identified research data will be maintained for 3 years following study closure.
--	--	--

Safeguards for Protecting Subjects Relative to Reasonably Expected Risks:

The principal investigator will be responsible for the protocol safety monitoring. The PI will make study documents (e.g., consent forms, data pulls) and pertinent hospital or clinical records readily available for inspection by the 59 MDW IRB and over sight staff for confirmation of the study data. If at any time the parent reports a side effect being experienced by their child, they will be referred to one of the Investigators for care or to the child's pediatric PCM.

Categories of subjects

Children (17 yrs or less), includes viable neonates (28 days of age to 12 months)

Clinical Care:

All children will receive standard of care regardless of inclusion into this study. If at any time a child experiences any injury or adverse effects, appropriate clinical care will be given or the child will be referred to appropriate provider. If a urine sample should be abnormal the PI or AI will follow up with the child's parents and ensure they either follow up with their primary care provider or report to the emergency department, if symptomatic.

Injury Compensation: N/A**Data Safety Monitoring**

N/A – none of the situations listed above apply

5. ALTERNATIVES**Alternatives:**

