The alternatives for QW urine collection are urine specimen collection by using the bag specimen collection method or the invasive straight catheterization or suprapubic aspiration. The alternative to using an iodine cleansing solution is to use a normal saline solution. The parents also have the authority to deny their child's participation in the study.

6. DATA ANALYSIS**Data Analysis:**

Primary analysis will be performed by intent-to-treat including all randomized children, where primary outcome data are available, consistent with the CONSORT guidelines for intention to treat analysis. The primary outcome measure is a binary yes/no outcome of detection of microbial markers to determine level of contamination. The absolute difference between the two groups will be reported so that the percentage of contamination samples, together with the 95% CI for the differences of percentages, and calculate p values using a chi squared test. A p value of <0.05 will be considered significant. For the secondary outcome there will also be a measure of binary yes/no outcome of voiding urine within 5 minutes. The rate of successful voiding within 5 min will be described for each group with percentages and 95% CI. The p value will be estimated using chi squared test for categorical variables and t-test or Wilcoxon's rank sum tests for continuous variables.

Additionally we will also be evaluating patient's gender, and age in months for comparative data analysis to help strengthen the study's statistical design outcomes.

Outcome Measures:

Level of urine contamination (binary yes or no), if there was a sample collected in 5 minutes (binary yes or no), and time to void with a 300 second cap are the two outcome measures being evaluated in this study.

Sample Size Estimation/Power Analysis:

This is a pilot study and will have a relatively low sample of 60 subjects.

Statistical Analysis:

Data analysis will be conducted by Baylor University statistics department ([name])

Number of Subjects:	# Planned to Enroll	# Enrolled	# Planned to Complete Study	TOTAL
----------------------------	----------------------------	-------------------	------------------------------------	--------------

Number of Subjects at 99 MDG	60	0	60	60
------------------------------	----	---	----	----

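### The plan names skin irritation and allergic reaction as iodine risks but reports reactions for no exposed child, and one of its rules discards the data of children who react

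*Combined protocol and SAP*

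**What the plan says.** **Risks.** Section 4 (Risks) states that "the only possible negative outcome could be skin irritation from the iodine prep group", and then adds a second risk: "There is a possibility that the child has an allergic reaction to the iodine swab".

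**A reaction during the procedure.** Two places deal with this. Section 3 (Research Design and Methods) has staff cleanse the area with saline and evaluate the child, after which the urine and the child's data are disposed of and excluded. Section 4 (Risks) refers the child to the primary care manager and keeps the sample in the study.

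**No sample at five minutes.** Section 3 says "it will be documented as a failure and the child will be referred back to their pediatric PCM and removed from the study". This applies to both arms.

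**What is recorded.** Section 3 describes three entries on the data sheet: time to void, whether the urine was caught, and whether the laboratory called it contaminated. The parent then completes a survey on overall satisfaction. The table of research material lists only the urine specimen, the data sheet and the survey.

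**What is reported.** Section 6 (Outcome Measures) lists contamination, sample within five minutes and time to void, and says these "are the two outcome measures being evaluated in this study". The Data Analysis text contains no summary of reactions or adverse events.

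**Safety oversight.** Section 4 makes the principal investigator responsible for safety monitoring. It opens a passive route, "If at any time the parent reports a side effect being experienced by their child", which leads to referral to an investigator or to the primary care manager. Data Safety Monitoring is marked not applicable.

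**The concern.** The trial is meant to show that iodine preparation makes clean catch an acceptable method in infants. If contamination falls, the next question will be how many infants reacted to the preparation. Every iodine child is exposed before collection begins, so the natural denominator is all children prepped with iodine. The plan provides neither a numerator nor a rule for that denominator.

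The disposal rule makes this worse. A missing safety table can sometimes be rebuilt from source data afterwards. It cannot be rebuilt if the data of the children who reacted have been disposed of. A later statement that no reactions were seen would then be a product of the rule and not a finding.

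**Working it through.** The plan gives no reaction rate or safety sample size, so there is no figure to reproduce. The check has two parts.

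**1. Tracing a reaction through the text**

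| Step | Source | Result |
|---|---|---|
| Is reaction a named risk? | Section 4, Risks | Yes, two kinds |
| Is there a described data entry? | Section 3, recording text | No (form not shown) |
| Is there a scheduled skin check after the procedure? | Sections 3 and 4 | No, for any child |
| Does a parent report become a study datum? | Section 4, Safeguards | Referral only; no recording step stated |
| Are a reactor's data kept? | Section 3 against section 4, Risks | Contradictory |
| Is there an outcome or analysis? | Section 6 | None |

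The answers are the same whether or not the child voids. The rule for reactions during testing covers every iodine child, and a child who does void adds only void time, catch and a later laboratory result.

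**2. What can be estimated, and what disposal does to it**

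Inputs: 60 children in total (section 6: "This is a pilot study and will have a relatively low sample of 60 subjects"). The allocation ratio is not stated (section 3 says only that "children will be randomly assigned to one of the two treatment groups"), so 30 iodine children is an assumption of 1:1 allocation.

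With zero reactions in n children, the one-sided 95% upper limit is 1 − 0.05^(1/n).

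- n = 30: 1 − 0.05^(1/30) = 9.5%.
- If the split were uneven, n = 25 gives 11.3% and n = 35 gives 8.2%.
- The upper end of a two-sided 95% interval at n = 30 is 1 − 0.025^(1/30) = 11.6%.

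Now suppose k of the 30 react during testing. The plan gives no expected rate, so k is illustrative. With all data kept, the estimate is k/30 with a one-sided exact (Clopper–Pearson) upper limit. Under the section 3 disposal rule the analysable result is always 0 out of 30 − k, with limit 1 − 0.05^(1/(30 − k)).

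| k (assumed) | Data kept: rate (upper limit) | Data disposed of: rate (upper limit) |
|---|---|---|
| 1 | 1/30 = 3.3% (14.9%) | 0/29 = 0% (9.8%) |
| 3 | 3/30 = 10.0% (23.9%) | 0/27 = 0% (10.5%) |
| 6 | 6/30 = 20.0% (35.7%) | 0/24 = 0% (11.7%) |

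For reactions during testing, the count after disposal is zero whatever happened. In the last row its upper limit, 11.7%, lies below the 20.0% actually seen. If section 4 (Risks) governs instead, the sample is kept, but there is still no described entry or analysis for the reaction.

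**The case against.** The best defence is that this is a 60-child pilot on contamination, using a solution that the protocol describes as standard. On that view, passive safety monitoring is proportionate. The principal investigator is responsible for safety, a side effect may be reported at any time, an investigator may be the one who receives it, and nothing excludes children who have been removed. The Participant Data Sheet, flow chart and consent form are attachments that are not shown, so a reaction field may exist.

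Much of this stands. It limits the severity of the point, and it means that absence of recording cannot be proved. It does not supply a reported result. Even if the form has a reaction field, section 6 plans no use of it, and section 3 would discard it for exactly the children who react.

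A reader might also infer a stronger point: that removal at five minutes cuts short safety observation for the children who do not void. On the earlier trial's success rate ("has been shown to significantly increase the five minute voiding success rate for CC urine collection; 31%, n= 174"), that would be 1 − 0.31 = 69% of those exposed. The documents do not support this. Children who void have no later skin check either, the rule for reactions during testing covers both groups, and a child who does not void is attended for the full five minutes. The parent-report route stays open after removal. The missing check concerns every exposed child, and the removal rule is not its cause. The 69% is also a projection from one earlier trial without a stated link to iodine preparation. For the same reason, the children who give a sample should not be treated as the safety denominator; nothing in the plan restricts observation of reactions to them.

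**Conclusion.** The point holds as a reporting and data-retention gap affecting all iodine-exposed children. The plan names two iodine risks and provides no outcome, analysis or described data entry for them. Sections 3 and 4 contradict each other on the data of a child who reacts. Under section 3, the count of reactions during testing is forced to zero.

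The removal wording contributes one ambiguity. The five-minute success rate requires failures to stay in the data, so removal cannot mean erasure of everything, yet the text does not say that safety data are kept.

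The size is modest. With an assumed 30 iodine children and complete recording, zero reactions would exclude rates above 9.5% (one-sided 95%); the present plan supports no such statement. This rests on 1:1 allocation and on the recording described in the body text, because the form itself could not be seen. The change is worth making before enrolment, since analysts cannot recover data that were never recorded or were destroyed.

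**What to change.** 1. **Record.** Add skin reaction yes/no to the Participant Data Sheet, completed at the end of the procedure for every child who received either preparation, including those without a sample at five minutes and those who react. Repeat the question on the Satisfaction Survey.
2. **Report.** In section 6, add the number, percentage and 95% CI of children with a reaction, by arm, among all children prepped. State that reactions appearing after the child leaves are captured only by parent report.
3. **Reconcile.** Bring section 3 and section 4 (Risks) into agreement so that reaction data are kept for the safety summary, whatever the sponsor decides about the urine sample.
4. **Clarify.** State in section 3 that removal at five minutes ends the collection attempt and not the retention of safety data.

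The cost is protocol wording, one extra item on two existing forms and one table row, with no added children or visits. Families of children who do not void must also answer the survey question. The change will not detect delayed reactions that parents do not report; it makes the reactions seen during the visit countable over the correct denominator.

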Children will then have their periurethral region gently cleansed for ten seconds with one of the previously discussed solutions. The procedure requires cold saline (approximately 2°C) soaked gauze to be applied in a circular motion over the bare suprapubic region of the child continuously for five minutes. The saline will come in the form of sterile saline flushes kept in a cooler of ice in the departments were the study is being conducted.

If the child voids within five minutes the time in seconds will be recorded on the provided worksheet. Also whether or not the urine was successfully “caught” in the specimen cup will be documented. Whether or not the sample was contaminated by lab standards will also be recorded on the data sheet once the results are available.

At the conclusion of the child's participation, the parents will be asked to complete a Satisfaction Survey asking their overall satisfaction with the collection method utilized.						
a. Interventions and Observations:						
The primary outcome of this study is to evaluate whether there is an improvement in the rate of urine contamination with iodine solution over normal saline prior to the QW. The secondary outcome will be the QW's rate of success in providing a CCU in five minutes.						
b. Setting:						
This study will be conducted at the 99MDG at Nellis AFB. Children will be recruited from the emergency department as well as the pediatric clinic through parental permission and consent. Research Staff will enroll children through parental authorization, based on the child's age, and if a standard of care urinalysis will be needed during their course of treatment, based on the determination of the child's attending physician. If a urinalysis is not needed as a course of treatment for the infant, the child will not be accepted for the study.						
c. Date(s):						
11 January 2019 – 31 May 2019						
d. Subjects:						
The sample population for this study are DoD beneficiary children from 28 days of age to 12 months requiring a standard of care urinalysis procedure as a course of treatment. They will be patients enrolled at 99MDG for evaluation and treatment. Children will be recruited from the pediatric clinic as well as the emergency department through parental permission and consent.						
e. Inclusion/Exclusion Criteria:						

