4. HUMAN SUBJECT PROTECTION

Recruitment and Consent Processes:
All potentially eligible childrens' parents will be approached to have their child participate. Primary Care Manager (PCM) referrals, with the patients' parents oral or written authorization, and posted advertisements will be utilized for recruiting children to the study. Some children may be patients of the PI or AI, however, they will have another study staff recruit the children through their parents to prevent any misconception of coercion or undue influence. When a potential child is identified by the treating PCM, their parent(s) will either be provided a contact number to the Research Staff, the Research Staff will be given the potential subjects contact information by the PCM with the parent's oral or written authorization, or the Research Staff will speak with the child's parent(s) directly, if contacted by the parent.

Consent Processes:
Parental Informed Consent (ICD) and HIPAA Authorization (HIPAA) will be sought in advance from each prospective child's parent(s) and appropriately documented in accordance with 32 CFR 219.117. Potential childrens' parents will be notified about the study either through posted advertisements, verbally through their child's primary care manager, or upon check in at the clinic and will be given the opportunity to consent for the child by one of the referred study coordinators. The study coordinator will provide a written copy of the Parental Informed Consent Document and HIPAA Authorization. The potential child's parents may decline to consent for the child without prejudice. At the parent's discretion, they may take the ICD and HIPAA home to discuss further prior to making a decision. If the parent consents to having their child enrolled in the study, a copy of the ICD will be given to them. Each parent will be asked to allow us to include their child's de-identified research data into the "Mike O'Callaghan Military Medical Center General Research Data Repository (FWH20180064H)" for future research.

Recruiting Service Members	Will you be recruiting service members in a group setting?	 Yes	 No
-----------------------------------	--	------------------------------	--

Participation Compensation:

Children and parents will not be paid for participation in this study.

Assent Process:

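### The allocation envelopes hold different supplies in each arm and no matching is described, so sealing and opacity alone do not secure concealment

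*Combined protocol and SAP*

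**What the plan says.** Section 3 (Research Design and Methods) names one allocation mechanism, introduced with the words "Utilizing sequentially numbered opaque sealed envelopes (SNOSE". Every envelope holds forceps, gauze, an index card naming the group and giving the child's ID number, and the Participant Data Sheet. One item depends on the arm: "For the experimental group there will be a package of iodine swabs and the control will have a normal saline flush". The sentence that follows adds the data sheet as a further item inside the envelope, so the arm-specific supplies are naturally read as being inside too.

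On the saline, Section 3 says "the control group will be prepped with cold (2°C) normal saline". It then describes the stimulation used in both arms, with cold saline "soaked gauze to be applied in a circular motion over the bare suprapubic region of the child continuously for five minutes", and says the saline comes as "sterile saline flushes kept in a cooler of ice in the departments".

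On people and order, Section 3b says "Research Staff will enroll children through parental authorization". Section 8 has nursing staff perform the collection. No section says who prepares, holds or opens the envelopes. Section 4 requires written parental consent before any research activity begins.

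**The concern.** Concealment means that nobody who influences enrolment can know or guess the next assignment before the child is committed to the trial. Opacity stops someone reading the card through the paper, sealing stops undetected opening, and numbering fixes the order. None of the three deals with contents that differ physically between arms. A package of swabs and a fluid-filled flush can differ in weight, shape and feel.

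If the next arm can be sensed, the decision to enrol a child, or its timing, can depend on that arm. The two groups may then differ at entry in ways that randomisation was meant to prevent. Section 6 plans a chi-squared comparison of contamination rates at p<0.05 and describes no adjusted primary analysis, so an imbalance at entry would pass straight into the result.

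**Working it through.** The plan states no figure on this point, so the check is a comparison of the text, followed by one calculation for scale.

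**1. Do the envelopes differ on each reading of where the flush is kept?** Section 3 puts a flush in the control envelope and has the control prep cold. The later sentence in the same section keeps saline flushes on ice.

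| Reading | Iodine envelope | Control envelope | Same in both arms? |
|---|---|---|---|
| Packed as written | swabs | flush | No |
| Control-prep flush taken from the cooler at use | swabs | no prep item | No |
| Control envelopes themselves kept cold | swabs, not chilled | flush, chilled | No; place or temperature also marks the arm |

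The cooler does not in itself reveal an arm, because both arms need cold saline for the suprapubic stimulation. The difference lies in the envelopes.

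**2. Is matching described anywhere?** The protocol body mentions no dummy item, padding, rigid outer pack or separate holding of supplies. The flow chart and data sheet listed in Section 12 are not reproduced, so they could not be checked.

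**3. What limits the opportunity to steer enrolment?**
- Section 4 says "All potentially eligible childrens' parents will be approached to have their child participate".
- Section 3 offers participation only to children "meeting the inclusion/exclusion criteria will be offered an opportunity to participate".
- Section 4 puts written consent ahead of any research activity.

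These lower the risk, but room for judgement remains. Under Section 3e the treating clinician may find a need for immediate treatment and invasive collection, which excludes the child. Under Section 4 parents may take the consent form home before deciding. Section 3 also asks about past iodine reactions before a child is placed in the experimental group, which can be read as a check made once the arm is known.

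**4. Scale only, not an estimate of bias.** Inputs: 60 subjects (Section 6), and 31% from the background in Section 2, read as the five-minute success rate. Equal allocation is assumed, since no ratio is stated.
- All give a sample: 60/2 = 30 per arm; one child's result moves that arm's contamination rate by 1/30 = 3.3 percentage points.
- 31% give a sample: 60 × 0.31 = 18.6, or 9.3 per arm; one result moves the rate by 1/9.3 = 10.8 percentage points.

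The same arithmetic holds under perfect concealment. It shows only how few altered enrolments would be visible in the result.

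**5. A related contradiction.** Section 3 places a child with a past iodine reaction in the saline group. Section 3e excludes children with past hypersensitivity to iodine swabs. The two conflict at least for children who reacted to swabs; for other iodine reactions the scope is unclear. The Section 3 rule is also a non-random route into the control arm.

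**The case against.** The strongest reply is that different contents are not the same as detectable contents. Every envelope also holds forceps, gauze, a card and a data sheet, which may mask a thin swab package, and matching may be set out in an attachment that is not available. This stands as a limit: the text shows that contents differ and that no matching is described. It does not show that anyone could tell the arms apart.

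A second reply is that both prep items could be department stock, chosen after the card is read, since Section 8 has nurses instructed when to use each one. The text does not strictly exclude this, but it runs against the list of envelope contents in Section 3. The cooler sentence may also refer only to the stimulation saline. The tension then lies between a cold control prep and a flush packed in an envelope, and it still needs resolving.

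Other provisions also help. The attending physician, not the enroller, decides that a urinalysis is needed; the investigators' own patients are recruited by other study staff; and sex and age will be compared between groups. None of these hides the next assignment.

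That the trial is non-blinded is no answer, because concealment concerns the time before assignment. Open use adds to the risk, since staff see each envelope's contents and can learn which feel goes with which arm. Nor does pilot status remove the point: the stated aim is comparative and a significance test is planned.

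**Conclusion.** The concern holds. As written, the only stated allocation mechanism puts different objects in the two arms' envelopes and relies on features that do not hide that difference. Confidence is high that this is what the plan describes. That staff could sense the difference is an inference, no breach is shown, and the size of any bias cannot be computed; the per-child figures carry no weight in this conclusion. It rests on the natural reading of the Section 3 contents list and on the absence of any matching in the available text. The change should be made, because it is cheap and removes a route to selection bias. The contradiction over past iodine reactions is a separate side point that needs reconciling, and no view is taken here on which rule should stand.

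**What to change.** Amend Section 3 so that every envelope has identical contents: the allocation card and the Participant Data Sheet only. Keep swabs, flushes, gauze and forceps as department stock, collected after the envelope is opened. Alternatively, use identical rigid packs with matched contents in both arms.

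In the same amendment:
- name one storage place for the control-prep flush, so that the two statements in Section 3 agree;
- state outright the order the protocol already implies, that the next numbered envelope is opened only after consent and eligibility are recorded;
- say who holds and who opens the envelopes;
- reconcile Sections 3 and 3e on past iodine reactions.

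The cost is repacking, holding stock in the pediatric and emergency departments, and short text edits. Sample size does not change. Collecting supplies after opening adds a small risk of picking up the wrong prep, which the staff training already planned in Section 8 can cover. Matched packs avoid that step but take more assembly.
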